1. INTRODUCTION

1.1 Study Purpose

Medtronic, Inc. is sponsoring Integrated Diagnostics Driven Diuretic and Chronic Medication Management for Heart Failure (INTERVENE-HF), a prospective, non-randomized, multi-center, feasibility study. The purpose of this clinical feasibility study is to gain experience with a research system that combines a device diagnostic based risk stratification algorithm with a guided work flow process managed by a centralized communication center. Findings from this feasibility study will be used to guide subsequent efforts to develop a heart failure patient management solution that may include integrated device diagnostics, a centralized communication center and medication intervention as key components.

1.2 Study Description

The INTERVENE-HF study is a prospective, non-randomized, multi-center (US only), investigational, feasibility study. Patients with heart failure that have an implanted commercially available Medtronic cardiac resynchronization therapy defibrillator (CRT-D) device will be enrolled in the study. The basic INTERVENE-HF research system is comprised of the pre-existing Medtronic, CRT-D device, investigational 2090 programmer software capable of turning ON/OFF the silent OptiVol[®] wireless CareAlert, and the INTERVENE Study Communication Center (ISCC). The ISCC will reside with the Care Management Service (formerly Cardiocom) business unit of Medtronic. The INTERVENE-HF study will have a dedicated team of licensed nurses at ISCC that will guide and monitor subjects through an individualized, physician prescribed medication intervention for diuretics and other acute volume management drugs after their silent OptiVol CareAlert has been transmitted and medication intervention is warranted.

The study is expected to be conducted at up to 20 centers located in the United States. Up to 400 subjects will be enrolled to yield up to 200 eligible subjects that meet screening criteria. This study will be conducted in subjects with an implanted, commercially available, Medtronic, CRT-D device. A detailed list of these devices and model numbers is provided in Table 4. To ensure a widespread distribution of data and minimize center bias in study results, the maximum number of subjects enrolled at a single center is 30 subjects. It is estimated that subject enrollment will take approximately 12 to 18 months. Each enrolled subject will be followed every 2 months from time of enrollment to end of the study. It is anticipated that subjects will participate in the study for a minimum duration of 12 months and up to approximately 30 months. The study will end after the last enrolled subject completes the 12-month follow-up. Because INTERVENE-HF is a feasibility study, it is not intended to show an outcome of improvement. Rather the objective is to test the operational feasibility and safety of device diagnostics *plus* an intervention system as set forth in the primary and secondary objectives. Interim analyses of these objectives will take place and if data are deemed to sufficiently characterize the study objectives by the sponsor at one of these analyses, enrollment and/or follow-up will be stopped.

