6.1 A) Screening Visit

6.1.1 Patient Informed Consent & Screening

The consent and screening process will take place prior to the baseline & programming visit. Bloodwork and CRT-D device values will need to be verified for study eligibility. These values

and procedures are described in section 7.7. If the subject does not meet eligibility, the subject will be exited and documented as a screen failure.

6.2B) Baseline & Programming Visit

6.2.1 Investigator Writes Standing Order for Medication Intervention and Establishes Subject Specific Safety Parameters

Once the subject has completed the consent and screening processes the subject's investigator will conduct the baseline visit. At this baseline visit the investigator will create an individualized medication intervention plan that is customized to the subject. This physician prescribed medication intervention plan is focused on the use of routine volume management medication, i.e. a transient elevation in diuretics or other volume management drugs (e.g. nitrates), and will include instructions for changes in the subject's diuretic dose for up to two rounds of medication intervention during a single episode. (One round = 3 days of taking medication that was prescribed at baseline. Two rounds = 6 days of taking baseline prescribed medication). This medication intervention of transient increase in volume management drugs is referred to as PRN (*pro re nata* or 'as needed') in the remaining text below.

Prescription(s) and adequate refills will be provided to the subject by the subject's primary care provider or investigator. The subject's individualized medication intervention plan will reside on file at the subject's participating clinic/hospital and also at the INTERVENE Study Communication Center (ISCC). The investigator (or responsible care team provider under the supervision of investigator) will be allowed to make changes to this prescription any time they deem necessary and will be required to notify ISCC with any changes within 24 hours with supplied forms.

In addition to the customized medication intervention plan, the investigator will collect information on the subject's chronic baseline medication and establish subject specific safety parameters for blood pressure changes and weight loss thresholds.

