7.3. Center Pooling

This study could include up to 20 US centers. Data from all the centers will be pooled. For each study objective, center effect will not be considered in the statistical modeling. Instead, for the two primary objectives, the average number of PRN interventions per subject that are effective or safety will be reported for each individual center. Using the effectiveness endpoint as an example, first the percentage of PRNs being effective will be calculated for each subject as the number of effective PRNs divided by the total PRNs that have been implemented for that subject; then the individual percentages will be averaged within each center. Center-specific analysis will not be conducted for the ancillary objective.

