7.9.1.4. Analysis Methods

For each episode that requires intervention as determined by this protocol, the effectiveness of Integrated Diagnostic Medication Intervention Strategy will be evaluated as a binary outcome variable, where 1 = effective and 0 = not effective. During the course of the study, a subject could experience more than one intervention. Therefore, a generalized linear model with the generalized estimating equation (GEE) method will be used to analyze this correlated binary data. The effectiveness rate and its 95% confidence interval (CI) will be calculated based on the log of odds estimated using the GEE.

In the main analysis, there will be no covariates in the generalized linear model, only intercept (β_0) will be estimated. Let π = probability (Integrated Diagnostic Medication Intervention Strategy is effective), then:

$$\beta_0 = \log\left(\frac{\pi}{1 - \pi}\right)$$

To solve for π :

$$\pi = \frac{e^{\beta_0}}{1 + e^{\beta_0}}$$

The analysis will be conducted using PROC GENMOD procedure in SAS similar to the following:

```

proc genmod data=effectiveness descending;
  class pt;
  model effective = /dist=bin link=logit type3;
  repeated subject=pt /type=exch modelse;
  output out=predict predicted=pr_success lower=lower_CI upper=upper_CI;
run;

```

In this procedure, 'effective' is the outcome variable with 1=effective and 0=not effective. 'dist=bin' and 'link=logit' indicates this generalized linear model is based on a logistic regression for binomial distribution. In the 'repeated' statement, 'subject=pt' assumes observations from the same subject are correlated, and 'type=exch' means parameter coefficient(s) in the model will be estimated using GEE. 'predicted=' in the 'output' statement gives the estimated probability of Integrated Diagnostic Medication Intervention Strategy being effective, and its 95% confidence interval based on the parameter estimate of the intercept are from 'lower=' and 'upper='.

If it turns out that the majority of subjects included in the analysis received a single Integrated Diagnostic Medication Intervention, a sensitivity analysis will be conducted through the common logistic regression assuming independent interventions within the same subject. In addition, secondary analysis may be considered to explore the association of covariates such as NYHA class with the effectiveness endpoint.

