7.9.2.4. Analysis Methods

Similar to the effectiveness endpoint of Integrated Diagnostic Medication Intervention Strategy, the safety endpoint of Integrated Diagnostic Medication Intervention Strategy is a correlated binary outcome with 1=safe and 0=not safe. It will be analyzed using a generalized linear model with GEE method. The safety rate and its 95% CI will be calculated based on the log of odds estimated using GEE.

Similar to Section 7.9.1.4, the analysis will be conducted using PROC GENMOD:

```
proc genmod data=safety descending;
  class pt;
  model safe = /dist=bin link=logit type3;
  repeated subject=pt /type=exch modelse;
  output out=predict predicted=pr_success lower=lower_CI upper=upper_CI;
run;
```

where 'safe' is the outcome variable with 1=safe and 0=not safe.

Again, if it turns out that the majority of subjects included in the analysis received a single Integrated Diagnostic Medication Intervention, a sensitivity analysis will be conducted through the common logistic regression assuming independent interventions within the same subject. In addition, secondary analysis may be considered to explore the association of covariates such as NYHA class with the safety endpoint.

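### Both primary 95% CIs treat subjects of one centre as independent; a centre-clustered sensitivity interval would show the extra uncertainty if centres differ

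*Protocol*

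**What the plan says.** SAP 7.3 (Center Pooling) pools data from up to 20 centres: "For each study objective, center effect will not be considered in the statistical modeling". For the two primary objectives it offers a description by centre instead. Each subject's percentage of effective or safe PRNs is computed, and "then the individual percentages will be averaged within each center".

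SAP 7.9.1.4 specifies the effectiveness model: "there will be no covariates in the generalized linear model, only intercept" is estimated, with the statement "repeated subject=pt /type=exch modelse". SAP 7.9.2.4 uses the same statement for safety. The outputs are the two rates with their intervals: "The effectiveness rate and its 95% confidence interval (CI) will be calculated based on the log of odds estimated using the GEE" and "The safety rate and its 95% CI will be calculated based on the log of odds estimated using GEE".

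On the source of the intervention, Protocol 6.2.1 says that at baseline "the investigator will create an individualized medication intervention plan that is customized to the subject". The investigator also sets the blood pressure and weight-loss parameters for each subject. Table 11 prints nominal limits next to a field for physician-specified values. Protocol 11.3 lets clinics continue their own standard of HF care.

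Protocol 1.2 addresses centre influence through enrolment: "minimize center bias in study results, the maximum number of subjects enrolled at a single center is 30 subjects".

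**The concern.** The GEE allows for correlation between episodes of one subject, but takes subjects of one centre as independent. Three features of the design could make them alike:

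- One investigator, or a small group, writes the PRN plans at a site.
- The same people may set the stop limits, and stopping for a safety issue counts directly as not safe (Protocol 13.4.2).
- Effectiveness fails on an HF event treated with IV diuretics or inpatient admission (Protocol 13.3.2), and those are partly local care decisions.

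There is no hypothesis and no performance requirement for either primary objective, so the rate and its 95% CI are the whole inferential result. Protocol 5.1 and 13.1 say that the findings will guide planning of a pivotal study, which implies use beyond these centres. The sponsor may also stop enrolment or follow-up once the data are judged to characterise the objectives sufficiently. An interval that is too narrow would overstate what is known in both settings.

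**Working it through.** **1. The plan's own precision figures.** Protocol Table 19 (SAP Table 2) uses exact Clopper-Pearson limits for independent episodes. For 70 episodes at 0.7 these are 0.5787 to 0.8038, width 0.225, as printed. The other rows also reproduce. The expected crossings are 43 + 62 + 63 + 40 + 25 = 233, and 0.45 × 233 = 104.9, so about 105 treated episodes.

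**2. Design effect for centre.** With K centres, m = 105/K episodes per centre on average and coefficient of variation cv of centre size:

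DE = 1 + [(1 + cv²)m − 1] × ICC

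Coverage of an interval that ignores centre ≈ 2Φ(1.96/√DE) − 1

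The documents give neither the ICC nor the cv; both are assumed. K = 20 is the planned maximum. K = 14 is the fewest centres that can hold 400 enrolled at 30 each (400/30 = 13.3).

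| Centres | m | cv | Coverage, ICC 0.02 | Coverage, ICC 0.05 | Coverage, ICC 0.10 |
|---|---|---|---|---|---|
| 20 | 5.25 | 0 | 94.0% (DE 1.085) | 92.5% (DE 1.212) | 89.9% (DE 1.425) |
| 20 | 5.25 | 0.6 | 93.6% (DE 1.123) | 91.4% (DE 1.307) | 87.7% (DE 1.614) |
| 14 | 7.5 | 0 | 93.5% (DE 1.130) | 91.1% (DE 1.325) | 87.3% (DE 1.650) |

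Worked example, second row at ICC 0.05: (1.36 × 5.25 − 1) × 0.05 = 0.307, so DE = 1.307, √DE = 1.143 and 1.96/1.143 = 1.71, giving 91.4%. For the same balance between centres, 14 centres give somewhat lower coverage than 20.

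**3. Simulation.** The formula ignores within-subject correlation, so the result was checked by simulation with these inputs:

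- From the documents: 200 programmed subjects, 55% with a crossing, the 39/28/19/9/5% distribution, 45% of crossings treated.
- Assumed: true rate 0.80, within-subject ICC 0.10, 20 unequal centres.

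Logit-scale sandwich intervals were computed with clustering on subject, and again with clustering on centre (variance × K/(K−1), t quantile with K−1 df, K = centres with an episode).

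| Centre ICC | Coverage, subject-clustered | Coverage, centre-clustered |
|---|---|---|
| 0 | 95% | about 94-95% |
| 0.02 | 94% | about 94-95% |
| 0.05 | 91% | about 94-95% |
| 0.10 | 87-88% | about 94-95% |

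An exchangeable GEE, the working correlation that the SAP names, covered 90.2% at ICC 0.05 and 87.2% at 0.10, so the choice of working correlation does not explain the loss.

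**4. Dependence on the rate.** At a true rate of 0.9, the subject-clustered interval covers 95.2% at ICC 0.01, 92.0% at 0.05 and 88.7% at 0.10.

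**The case against.** Much of the design pulls centres together. All subjects have one OptiVol threshold, fixed risk cut-offs, a central nurse team following one workflow, a single recovery criterion and CEC adjudication. PRN plans and limits are specific to the subject, and Table 11 offers common defaults. Variation between subjects is already covered by clustering on the subject. No passage shows that centres differ materially. All of this stands. It argues for a low ICC, although it does not show that the ICC is zero.

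The choice is also openly declared, in a feasibility study whose first purpose is to gain experience. If the target is only the centres enrolled, the undercoverage does not arise. That stands too, so the point is tied to use of the interval beyond these centres.

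The effect is small at the first interim. With 100 subjects (about 53 episodes) and 20 centres, simulated coverage was 93-95% at ICC 0.05 for rates of 0.8 to 0.95.

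Three stronger readings are tempting but not supported:

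- A reader might infer that any centre correlation pushes coverage below 95%. At a rate of 0.9 and ICC 0.01 it was 95.2%.
- A reader might infer from the cap that all 200 programmed subjects could come from 7 centres (200/30 = 6.7). That needs nearly every consented subject to pass screening, whereas the plan allows for 400 enrolled to yield 200.
- A reader might take the cap as a failed variance correction. Protocol 1.2 presents it as a way to spread data and limit bias, and makes no claim about interval width.

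**Conclusion.** The point holds in a limited form. Neither primary interval contains between-centre variation, and the documents give plausible reasons why some may exist. Under the assumptions above (20 unequal centres, rate 0.80, within-subject ICC 0.10), the loss of coverage is about 1 percentage point at centre ICC 0.02, 4 points at 0.05 and 7 to 8 points at 0.10. For the same balance it is somewhat larger with 14 centres. The centre ICC is wholly assumed, and the centralised workflow makes the lower values credible.

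The consequence is overstated precision only. With no hypothesis or success threshold, no decision error rate changes. The planned subject-clustered analysis is defensible as the main analysis, and nothing here requires replacing it. This is a cheap improvement.

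**What to change.** Keep the subject-clustered GEE as the main analysis. Add to SAP 7.3, 7.9.1.4 and 7.9.2.4 a named sensitivity analysis for both primary rates:

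- cluster on centre, which also covers within-subject correlation because subjects are nested in centres;
- independence working correlation;
- sandwich variance multiplied by K/(K−1), and a t quantile with K−1 degrees of freedom, where K is the number of centres with at least one episode;
- reported beside the main interval at both interim analyses of the objectives and at the final analysis.

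The cost is SAP wording and one extra model per endpoint, with no new data. The second interval will be wider. In the 20-centre simulation at rate 0.80, mean width goes from about 0.158 to 0.166 with no centre effect (0.166/0.158 = 1.05, about 5% wider), and from 0.159 to 0.192 at ICC 0.05 (0.192/0.159 = 1.21, about 21% wider).

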2. BACKGROUND AND JUSTIFICATION

Assessment of risk to guide appropriate medical care has become a necessary tool in the management of cardiovascular disease. Published guidelines for managing cardiovascular disease are based in large part on identifying subjects at risk and then treating patients in a manner to reduce that risk.¹ The development of risk prediction models for cardiovascular diseases dates back to at least the 1960s.^{2,3} Since that time, new and updated risk models have continued to be developed.⁴⁻⁷ Risk prediction models also exist for specific cardiovascular diseases. For example, the Seattle Heart Failure Model was developed to predict survival in patients with congestive heart failure⁸ and the CHADS2 score was developed to predict the risk of stroke in patients with atrial fibrillation.⁹

These risk models, while clinically useful, are generally static in nature and cannot necessarily respond to dynamic changes in the many factors that may impact patient risk. For example, these models can likely predict which patient is at higher risk of developing frequent HF worsening events, but when exactly such an event might occur temporally cannot be predicted. Because device diagnostics dynamically vary with patient status (see description of various device diagnostic parameters below), they have the potential to be a robust and dynamic cardiovascular risk assessment tool to help guide appropriate medical intervention.

CRT-D devices, such as those included in this study, collect valuable clinical diagnostics data. These diagnostic variables can be combined to generate patient risk status using a variety of methodologies. One methodology uses a Bayesian Belief Probabilistic model to categorize patients into three risk categories – Low, Medium and High. The details of the model have been discussed in a paper by Cowie et al.¹⁰ Briefly, the model uses 5 distinct variables as input - thoracic impedance, activity, heart rate variability, heart rate, and a combination variable based on arrhythmia and shock related information collected by the device. All of these variables have a mechanistic link with worsening heart failure, and several of them have been shown to have a prognostic value for heart failure event in the literature. Below is a brief description of each of the device variables that are input into integrated diagnostics algorithm.

- a. **Intrathoracic impedance (OptiVol):** As a patient's HF status worsens, it is generally associated with rise in atrial filling pressure and retention of fluid in the pulmonary circulation. If sustained over time, this can eventually lead to fluid infiltration into interstitial space, thus leading to worsening pulmonary congestion.¹¹ Since blood and interstitial fluid are highly conductive, their accumulation in the pulmonary system leads to a reduction in thoracic impedance. Thus, intrathoracic impedance appears to have mechanistic link with worsening HF.¹¹⁻¹³

- b. **Heart rate variability (HRV):** HRV is a marker of autonomic tone and has been shown to provide prognostic information for mortality risk.¹⁴ Research has demonstrated a correlation between the decrease in HRV and increased sympathetic tone. Cardiac resynchronization therapy, that has been shown to improve heart failure status, results in an increased HRV indicative of shift away from sympathetic

dominance.¹⁵ Using HRV device diagnostic data, Adamson et al.¹⁶ showed that patients with low HRV (<100 ms) are at a higher combined risk of death and hospitalization. The same study showed that patients with HRV < 50 ms were even at higher risk than those with HRV in the range of 50-100 ms.

- c. **Heart Rate:** Similar to HRV, elevated heart rate is a marker of elevated sympathetic tone and has been shown to have prognostic value for worsening HF. Night Heart Rate (NHR) (measured between midnight and 4 AM) is a better metric than the day time heart rate, which can be confounded by varying activity level (e.g. rest and exercise). A study in implantable device patients demonstrated that patients with high NHR (75±25 bpm) were at higher risk of being hospitalized or dying than those who had low NHR (73±11 bpm).¹⁶
- d. **Activity:** As patients retain fluid in the pulmonary circulation resulting in pulmonary congestion, they can easily develop dyspnea, thus limiting their functional capacity and activity level. In patients with a CRT device, patient activity declined from 188±109 min/day at baseline to 164±118 min/day at the time of hospitalization.¹⁶ Thus, decline in patient activity is associated with worsening HF status and potentially has value for predicting HF hospitalization.
- e. **Combination variable:** The final variable that is input into the integrated diagnostic algorithm combines pacing and arrhythmia related information. Specifically, one of the components of this variable is substantial decrease (>8%) in CRT pacing, which is associated with high HF events.¹⁷ A decline in CRT pacing can occur because of rapid conduction during AF. Thus, mean ventricular rate \geq 90 bpm and atrial fibrillation (AF) burden \geq 6 hours/day and shocks delivered to Ventricular Fibrillation/Ventricular Tachycardia (VT/VF) are also components of this variable.

Each of the five variables input into the Heart Failure Risk Status - Integrated Diagnostics Algorithm (ID1.0 HFRS-ID) has a prognostic value for HF. Combining these variables into a single HF risk metric yields a prognostic indicator that is better than each of the individual components alone because these variables capture slightly orthogonal information (e.g. while decrease impedance is an indicator of elevated pulmonary pressure, HRV is an indicator of autonomic imbalance), and hence add to provide a better overall snapshot of patient status. Our model development data indicate that a patient with a risk score in the 'high' group were 10 times more likely to have an Heart Failure Hospitalization (HFH) in the next 30 days compared with 'low' risk patients.¹⁰ A patient with 'medium' risk status is at 2x higher risk of hospitalization in the next 30 days.¹⁰

While a high performance diagnostic is necessary for effective HF patient management, previous clinical trials have shown that diagnostic information alone is not sufficient to improve patient management. For example, the COMPASS-HF¹⁸ and REDUCE-HF¹⁹ trials that provided clinically relevant estimated pulmonary artery (PA) pressure measurements to physicians for HF management did not show statistically significant difference in HF based outcomes between PA pressure management arm and control arm. This lack of outcome improvement was attributed to lack of clinical actions in response to changes in PA pressure.

In contrast, in the CHAMPION trial²⁰ using another version of a PA pressure measuring device, the treatment arm using PA pressures to manage patients yielded a significant decrease in HF events compared to the control arm (~30% reduction at 6 months and 40% reduction at 15 months in HF hospitalization). In addition, alert mechanism and workflow are also important as they can influence healthcare utilization.²¹ The key attribute of the CHAMPION trial that presumably led to positive outcome results was that actions to control the PA pressure were in fact mandated as part of the trial. And in fact, CHAMPION reported significant medication changes from the baseline not only in the diuretic doses, but also in other medications such as beta-blockers, ACE inhibitors, Angiotensin receptor blockers and nitrates among other drugs.^{18, 19}

Therefore, combining a prescribed medication regimen with a diagnostic variable seems to be a necessary condition to drive actions and improve patient outcomes. Thus, the goal of the INTERVENE-HF study is to test the feasibility of combining an integrated device diagnostics-based risk stratification algorithm with a guided work flow process managed by a centralized communication center. INTERVENE-HF is a feasibility study with a single-arm design and a limited number of subjects, and is not intended to show an outcome of improvement. Rather, the objective is to test the operational feasibility of diagnostics plus an intervention system, and quantification of the operation effectiveness and safety as set forth in the primary and secondary objectives.

